Aim 1: Adapt a previously validated machine learning algorithm to predict risk of colorectal cancer or adenoma among a retrospective cohort of Penn Medicine patients living in vulnerable zip codes within Philadelphia County. We will improve upon a previously validated machine learning algorithm¹ to predict risk of colorectal cancer by (1) re-training the model to predict both cancer and adenoma detection; (2) integrating additional clinical and socioeconomic risk factors for colorectal cancer risk; and (3) retraining the model in a cohort of individuals living in Philadelphia County zip codes that are minority-predominant and have lowest median incomes in the county. We will compare algorithm performance to existing criteria, based on age and prior colon cancer screening history, which are currently used to stratify colorectal cancer risk among Penn Medicine patients. We hypothesize that machine learning models will maintain good performance in predicting CRC risk among a community living in a persistent poverty area.

Aim 2. Test the feasibility, usability, and effectiveness of algorithm-informed navigation on colorectal cancer screening rates and adenoma detection rates among Penn Internal Medicine and Family Medicine patients residing in racially and ethnically diverse zip codes. We will use the machine learning algorithm developed in Aim 1 to inform the CRC screening navigation program process and evaluate its impact on the identification of Penn Internal Medicine and Family Medicine patients with adenomas and CRC. We will generate automated monthly lists of Penn Medicine Internal and Family Medicine patients from diverse communities ranked by predicted cancer risk. High-risk patients will be prioritized for navigation of socioeconomic and financial barriers to colonoscopy through an existing navigation program created and managed by our team at the University of Pennsylvania.² In addition to assessing feasibility and usability, we will evaluate the effectiveness of the program on rates of completed colonoscopies and rates of CRC/adenoma detection, compared to historical rates prior to the intervention. We hypothesize that algorithm-informed navigation will improve CRC screening rates and cancer/adenoma detection rates.

Need for Cancer Control Program in Philadelphia County

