While colorectal cancer screening may reduce cancer-associated mortality, African-Americans in Philadelphia County are over 10 percentage-points less likely to be adherent to colorectal cancer screening guidelines compared to Whites. Despite the proven benefit of regular colonoscopy, CRC screening adherence rates remain only around 50% for Penn Medicine primary care patients. Furthermore, screening rates are consistently worse for African-Americans than White individuals – and this disparity is widening at Penn Medicine (Fig. 2). For this reason, Penn Medicine, a safety net provider for low income, underserved patients in Philadelphia, has instituted a system-wide goal of improving CRC screening for African-American patients.

Existing Services

Colorectal cancer screening navigator program: Adverse social determinants of health such as lack of transportation access contribute to CRC screening nonadherence disproportionately for African-American and other minority communities. Recognizing this, in 2011, Penn Medicine created a navigation program to address poor CRC screening rates and increase access to screening colonoscopies for patients in underserved areas of West, South, and Southwest Philadelphia.² The navigation program provides services to address barriers to cancer screening; these include transportation assistance, detailed instructions on bowel prep, or mailed FIT test for average-risk patients who refuse colonoscopy (see **Fig. 3**). Eligible patients have had a colonoscopy order placed in the past six months and have not scheduled, cancelled, or no-showed to their colonoscopy. Among eligible patients contacted by the navigator program, 50% agree to a colonoscopy over the phone. Of those patients, 80% complete a colonoscopy. The CRC screening navigator program is currently staffed by 1.5 FTE staff, including the nurse lead of the navigator program **[name]**, BSN, RN, OCN (see attached **Letter of Support**) and a part-time clinical assistant. Our prior research has shown that navigated patients have a high rate of colorectal cancer screening completion (79%) and a significantly lower rate of cancelled and/or skipped appointments.² In addition, those who were screened as a result of the program had a much higher

Figure 2. CRC screening in Philadelphia county

Program Director/Principal Investigator (Last, First, Middle): [name]

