The focus group will garner feedback about the intervention and strategies to integrate automated navigation services into routine workflow. This intervention will occur without physician referral; however, given that some automated predictions may be incorrect, we will display results from an algorithm that predicts both CRC and adenoma vs. a model that predicts CRC alone. We will elicit perspectives from these clinic groups about which algorithm they agree with the most, in order to determine which algorithm to proceed with for Aim 2.

PDSA cycles: After training the algorithm, we will conduct a 3-month pilot using patients from one primary care practice, using the Plan-Do-Study-Act (PDSA) Framework¹³ to identify patient and clinic barriers to this research program. In the “Plan” stage, the critical elements are: (1) integrating flags for algorithm-predicted high-risk patients into existing automated lists given to the navigator program; (2) selection, training and defining the functions of the new CRC screening navigator; and (3) establishment of a network of clinic partners serving patients in the high poverty navigation program. The “Do” stage is focused on the implementation of an algorithm-facilitated navigation process to address the clinical and social barriers to CRC screening. The “Study” stage is defined by tracking enrolled patients and evaluating program measures that include completion of screening and adenoma detection rates and, then, in the “Act” stage, optimizing the program to expand the reach of the program to serve a broader population of patients, potentially even outside of Penn Medicine.

Approach

Aim 1. Validation of ML algorithm to predict colon cancer and adenoma risk

Study Design. Retrospective cohort study

Cohort. 60,270 unique patients without a prior CRC diagnosis who had a colonoscopy order placed by a Penn Internal Medicine or Family Medicine provider living in one of 18 minority-predominant zip codes in Western and Southwestern Philadelphia County; completed a colonoscopy at Penn between January 1st, 2010 and December 31st, 2019; and were seen by a Penn primary care physician in the preceding year. We will split the cohort into training (70%) and validation (30%) sets at the patient-level so that patients are represented in either the training or validation set only.

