Outcome. The primary outcome will be biopsy-proven CRC or adenoma, based on (1) diagnostic or procedural codes for CRC or adenoma using previously published administrative code mappings^{14,15}; and (2) internal datasets on Adenoma Detection Rate (ADR), generated by the Data Analytics Center using Provation and Clarity pathology data. Preliminary data suggest that 4,210 cases of CRC or adenomas exist in our cohort.

Predictors. We will use PennChart Clarity data from the 6 months prior to the colonoscopy as predictors in the model. Predictors will be adapted from prior literature and will include demographic (e.g. age, gender, EtOH history), comorbidity (e.g. anemia, inflammatory bowel disease), laboratory (e.g. hemoglobin, BUN), utilization (e.g. prior colonoscopy orders), and socioeconomic (e.g. area-level income and education) data.^{1,11,12} Additionally, we will use the EPIC social determinants of health tool to extract features such as income, education level, and homelessness that may be associated with CRC risk. .

Modelling strategy. We will compare the cross-validation predicted performance of several ML strategies, including logistic regression, random forest, gradient boosting, and recurrent neural networks, to identify the model with optimal predictive performance. We will report algorithm performance on the hold-out validation set, specifically testing for performance differences between the algorithms. Finally, we will compare performance of the best ML algorithm against an existing PennChart risk stratification model that uses only age and prior colorectal cancer screening utilization as predictors.

Performance metrics. Primary performance metrics will include area under the receiver operating characteristic curve (AUC), area under the precision-recall curve (AUPRC), and sensitivity.

Limitations. Administrative codes and internal ADR data may underestimate the true outcome rate, although the number of cases and event rate (7.0%) should still allow adequate model development.

Aim 2. Pilot testing of ML-facilitated colon cancer screening navigation

Study Design. Prospective cohort study with 3-month enrollment period and 3-month follow-up.

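### Aim 1 builds and tests the model on data up to the colonoscopy, but Aim 2 scores patients at monthly list dates when no colonoscopy has happened, so reported performance is not measured at the time of use

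*Combined protocol and SAP*

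**What the plan says.** **Aim 1, Cohort.** Each patient "had a colonoscopy order placed by a Penn Internal Medicine or Family Medicine provider" and "completed a colonoscopy at Penn between January 1st, 2010 and December 31st, 2019". The cohort is split 70/30 by patient into training and validation sets.

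**Aim 1, Predictors.** "We will use PennChart Clarity data from the 6 months prior to the colonoscopy as predictors in the model". The named inputs include anemia and "laboratory (e.g. hemoglobin, BUN), utilization (e.g. prior colonoscopy orders". No lag before the procedure is stated.

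**Aim 1, Modelling strategy and Performance metrics.** "We will report algorithm performance on the hold-out validation set, specifically testing for performance differences between the algorithms". The metrics are AUC, AUPRC and sensitivity. The best model is then compared with "an existing PennChart risk stratification model that uses only age and prior colorectal cancer screening utilization as predictors".

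**Specific Aims, Aim 2.** The Aim 1 algorithm is carried forward: "We will generate automated monthly lists of Penn Medicine Internal and Family Medicine patients from diverse communities ranked by predicted cancer risk".

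**Aim 2, Cohort and Intervention.** Listed patients have an order from the past 6 months and an unfilled colonoscopy. Each monthly list holds about 300 of them. The score, together with other high-risk criteria, sets the priority of outreach.

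No section gives the data cut-off for scoring a listed patient, or plans to report performance at a list date. The pilot described under PDSA cycles tracks screening completion and adenoma detection, not discrimination.

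**The concern.** A prediction model should be developed and tested at the moment when it will be used. Here the two moments differ by construction. In Aim 1 the look-back ends at a date that is known only because the patient completed the procedure. In Aim 2 the patient is scored because that event has not happened.

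Some predictors can change between order and procedure: a new hemoglobin or BUN, a new anemia diagnosis, a second colonoscopy order after a cancellation. In Aim 1 these enter both training and hold-out. On the list date for the same patient, some of them would not yet exist.

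Three uses depend on the Aim 1 metrics:
- They are the only planned test of the hypothesis that the model keeps good performance in this community.
- They decide the comparison with the PennChart model. Age, at least, moves little over a few months, so a timing effect could fall unevenly on the two models. How far it does depends on how prior screening utilization is defined, which the documents do not say.
- Results from the candidate algorithms are shown to clinic focus groups, which help choose the one for Aim 2.

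**Working it through.** **1. The plan's own figure.** Event rate = 4,210 / 60,270 = 6.99%, which agrees with the stated 7.0%. The hold-out is 0.30 × 60,270 = 18,081 patients with 0.30 × 4,210 = 1,263 cases. Hold-out size is therefore not the difficulty.

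**2. The two time points side by side.**

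| | Aim 1 training and hold-out | Aim 2 use |
|---|---|---|
| Patient state | Colonoscopy completed | Order open, colonoscopy not done |
| End of look-back | Colonoscopy date | Not stated; can be no later than scoring |
| Performance reported | AUC, AUPRC, sensitivity | None |

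The Aim 1 rule needs a date that no Aim 2 patient has.

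**3. How much of the window falls after scoring.** The documents give no order-to-procedure gap, so g (in months, 1 to 6) is an assumption. Order dates are assumed to be spread evenly over the month.
- First list date after the order: on average 0.5 month after it. Mean share of the 6-month window after scoring = (g − 0.5)/6.
- Last list date before the procedure: on average 0.5 month before it. Mean share = 0.5/6 = 8.3%, whatever g is, and at most 1/6 = 17%.

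| Gap g (months, assumed) | Last list date | First list date |
|---|---|---|
| 1 | 8% | 0.5/6 = 8% |
| 2 | 8% | 1.5/6 = 25% |
| 3 | 8% | 2.5/6 = 42% |
| 4 | 8% | 3.5/6 = 58% |
| 6 | 8% | 5.5/6 = 92% |

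A patient whose order stays open can appear on several lists, and one who schedules may leave the list early. The share in practice lies between the two columns.

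**4. Effect on AUC, AUPRC or sensitivity.** This cannot be derived, because the documents give neither the gap distribution nor performance by lag.

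**5. Precision of a re-anchored analysis.** The inputs are AUC 0.73 and sensitivity 0.44, from the CRC risk algorithm paragraph. The Hanley-McNeil 95% half-width for AUC and the binomial half-width for sensitivity are:
- Full hold-out (1,263 cases): ±0.016 and ±0.027; for sensitivity, 1.96 × √(0.44 × 0.56 / 1,263) = 0.027.
- A list-eligible subgroup of 20%, 10% or 5% of the hold-out (assumed shares) at a 7% event rate, with 253, 126 or 63 cases: AUC ±0.036, ±0.051 or ±0.072; sensitivity ±0.061, ±0.087 or ±0.122.

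**The case against.** **The effect may be small.** Many predictors (age, gender, alcohol history, inflammatory bowel disease, area-level income and education) hardly move over months. A share of the window is not a loss of performance, and if the last list date is the relevant one, only about 8% of the window is affected. All of this stands. It limits the size of the point, but it does not supply a scoring date or a measure of performance at it. It also means that no particular gap can be named as the threshold at which the issue becomes serious.

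**A reader might infer that the hold-out AUC is inflated.** That is plausible for time-varying inputs, but the documents do not show it. They support only that performance is measured at the wrong time point.

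**A reader might infer that using completers is itself the error.** The outcome needs a colonoscopy, so completers are unavoidable. The index date is avoidable, because every Aim 1 patient also had an order.

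**Past navigation may make the populations overlap.** Existing Services says that "in 2011, Penn Medicine created a navigation program to address poor CRC screening rates", so some 2010-2019 completers may have finished after an unfilled order. This supports little. The same section says that the program covered 5 zip codes until July 2015, 11 until January 2021 and 18 only after that, and that it currently serves Internal Medicine practices. If the 18 zip codes are those of Aim 1, 18 − 11 = 7 lay outside the program throughout the cohort period.

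**Outcomes are tracked later.** Adenoma detection is followed in the pilot and is an Aim 2 outcome. Neither measures discrimination at scoring.

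**Conclusion.** The point holds as a mismatch between a stated rule and the stated use. As written, the Aim 1 window cannot be reproduced for Aim 2 patients, and the planned metrics do not describe the model at the time it ranks them. It should be corrected before the Aim 1 data pull.

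On the stated assumptions, exposure starts at about 8% of the window; its upper end grows with the unknown gap. The conclusion rests on the plain reading that the window runs up to the colonoscopy. If a lag is intended, stating it would resolve part of the point.

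A reader might infer that the Aim 2 effectiveness result is compromised. It is not biased by this: that comparison is between navigated patients and historical controls and does not use the hold-out metrics. Nor do the documents say that a low score excludes anyone from navigation.

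**What to change.** 1. **Re-anchor Aim 1.** In training and hold-out, end the 6-month look-back at a simulated monthly list date on which the order was open and no more than 6 months old. Use all such dates, with intervals that account for clustering by patient, or one date chosen at random per patient. Order age then resembles the Aim 2 lists, which a first-list-date rule alone would not achieve. Pre-specify the anchor order: the one linked to the colonoscopy or, without a link, the most recent order before it. If no list date precedes the procedure, use that order's date. Report how many patients cannot be anchored.
2. **Use one rule throughout.** Score Aim 2 patients at their list date with the same look-back. Report hold-out AUC, AUPRC and sensitivity at that anchor for both the ML model and the PennChart comparator. Keep the colonoscopy-anchored result as a sensitivity analysis; the difference between the two shows how much the timing matters.
3. **Address the population as far as the data allow.** If order-status history exists, add the same metrics with 95% confidence intervals in completers who would have met the list criteria. In either case, state that performance in patients who never complete a colonoscopy is unknown.

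**Cost.** A changed data pull and an extra table. Some patients may lack a usable order date, since the cohort definition does not tie the order to the completed procedure. The reported AUC may change. Items 1 and 2 correct timing only. Item 3 depends on data whose availability is not documented, and its intervals will be wide if the subgroup is small.

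### The Aim 1 comparison with PennChart is a sound current-practice benchmark, but cannot show what ML and the added EHR predictors contribute beyond age and prior screening

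*Combined protocol and SAP*

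**What the plan says.** Specific Aims, Aim 1, describes two kinds of retraining for the ML algorithm. One is to the label: "re-training the model to predict both cancer and adenoma detection". The other is to the population: "retraining the model in a cohort of individuals living in Philadelphia County zip codes that are minority-predominant". Approach, Aim 1 (Cohort), assigns 70% of 60,270 patients to training and 30% to validation.

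Under Modelling strategy several learners are candidates, "including logistic regression, random forest, gradient boosting, and recurrent neural networks". The plan will then "compare performance of the best ML algorithm against an existing PennChart risk stratification model that uses only age and prior colorectal cancer screening utilization". Specific Aims calls the comparator "existing criteria, based on age and prior colon cancer screening history, which are currently used to stratify colorectal cancer risk among Penn Medicine patients".

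The documents do not say whether the comparator will be refitted. They also do not say whether it is a regression or a points rule, what outcome it was built to predict, or in whom it was developed. No analysis fits age and prior screening alone to the training set. Logistic regression is listed only as one of the ML strategies.

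**The concern.** As described, the two sides of the comparison receive different treatment. The gap between them can contain three components: fitting to local patients, fitting to the CRC-or-adenoma label, and the added EHR predictors with the ML method. Only the third shows that an EHR algorithm adds something to age and screening history. A two-predictor model given the same training data might close part of the gap.

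This is the only planned Aim 1 comparison against those two predictors. If the whole gap were reported as the gain from ML, the gain could be overstated. A simple, locally fitted rule that ranks patients nearly as well could also be overlooked.

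**Working it through.** **1. Inputs from the plan.** Cohort 60,270 and 70/30 split (Approach, Aim 1, Cohort); 4,210 cases (Outcome); event rate 7.0% (Limitations). Check: 4,210 / 60,270 = 6.985%, which reproduces the stated 7.0%.

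**2. Hold-out size.** Training: 0.70 × 60,270 = 42,189 patients, 0.70 × 4,210 = 2,947 cases. Hold-out: 18,081 patients, 1,263 cases, 16,818 non-cases.

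**3. Precision of an AUC difference.** Hanley-McNeil, with n1 = 1,263 and n0 = 16,818:

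SE² = [A(1 − A) + (n1 − 1)(A/(2 − A) − A²) + (n0 − 1)(2A²/(1 + A) − A²)] / (n1·n0)

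- A = 0.73 (the earlier ML version, Existing Services, CRC risk algorithm): SE = 0.0083.
- A = 0.65 (assumed for the comparator): SE = 0.0086.
- Paired difference, √(SE₁² + SE₂² − 2r·SE₁·SE₂): 0.0100 at r = 0.3 and 0.0066 at r = 0.7. Both correlations are assumed.

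**4. What refitting can change.** AUC and AUPRC depend only on how patients are ranked. Recalibrating the existing score would change neither. Refitting matters only if the tool weights or groups its two predictors differently from a model fitted to this cohort and label.

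**5. AUC gained by refitting the same two predictors, for different forms of the existing tool.** Assumptions: 7% event rate; age mean 60, SD 9; log-odds 0.02 to 0.06 per year; prior screening in 40%, with odds ratio 0.5 or 0.7. The points rules add one point if unscreened.

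| Assumed form of the existing tool | AUC gain from refitting |
|---|---|
| Continuous age, screening weight wrong by a factor of 0.5 to 2 | 0.000 to 0.008 |
| Five-year age bands, correct weights | 0.0005 to 0.0024 |
| Points rule, age cut at 50/60/70 | 0.007 to 0.024 |
| Points rule, age cut at 60 | 0.012 to 0.044 |

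In standard errors, the first two rows reach at most 0.008 / 0.0066 = 1.2. The points rules run from 0.007 / 0.0100 = 0.7 to 0.044 / 0.0066 = 6.7.

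**6. What this does to the reported gain.** A second simulation used N = 60,270, the 70/30 split and 10 runs per scenario. It assumed age mean 60 and SD 8, prior screening in 50%, log-odds 0.4 per SD of age and −0.6 for prior screening, and one extra predictor. The existing tool was a coarse tier (age 65 or over, plus unscreened).

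| Extra predictor, log-odds per SD | AUC: existing / refitted two-predictor / full | Gain over existing | Gain over refitted |
|---|---|---|---|
| 0 | 0.612 / 0.640 / 0.640 | 0.028 | 0.000 |
| 0.4 | 0.611 / 0.639 / 0.675 | 0.064 | 0.036 |

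In the first row the extra predictor carries no information, yet the full model leads the existing tool by 0.028. If instead the existing score ranks patients as a refitted one would, the two gains are equal and nothing is overstated.

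**The case against.** The strongest reply is that the plan asks how the algorithm compares with the criteria in use. For that question the unmodified tool is the right comparator and the result is not biased. The Aim 1 hypothesis is only that "machine learning models will maintain good performance in predicting CRC risk among a community living in a persistent poverty area"; it claims no superiority. This stands, and the PennChart comparison should stay.

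Several stronger readings are tempting but unsupported:

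- *The comparator is an off-the-shelf model that will not be refitted.* The text calls it existing and currently used for Penn Medicine patients, and is silent on refitting. Only the absence of a described refit can be stated.
- *Aim 2 depends on this result.* No section makes Aim 2 conditional on it. Under Focus groups, clinic feedback chooses between a CRC-plus-adenoma and a CRC-only algorithm. Work plan and timeline ties the later grant to the feasibility study as a whole.
- *A spurious significant result is built into the plan.* Testing is specified for differences between the candidate algorithms. For PennChart the plan says only that performance will be compared.
- *The artefact is large.* That presumes a coarse tool, and no section says that PennChart bands age.

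It is also fair that comparing logistic regression with the other learners shows what flexible methods add on the same patients and label. It does not isolate the added predictors, because the plan does not restrict that regression to age and prior screening.

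**Conclusion.** The point holds as a limit on interpretation. The planned contrast cannot separate the added predictors and ML method from local fitting to the study label, and no other planned analysis does so.

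The size cannot be fixed from the documents. Depending on the form of the tool, it runs from nothing, or about one standard error at most, to several standard errors of the hold-out difference. Apart from the cohort size, case count, event rate, split and AUC of 0.73, every input to that range is an assumption.

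A reader might infer that the PennChart comparison is invalid, or that any ML advantage is an artefact. The documents support neither. A change is worth making because the remedy costs very little, not because a large error has been shown.

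**What to change.** 1. Keep the PennChart model as the current-practice benchmark. State its form and target outcome, and whether it is used unchanged.
2. Add a logistic regression on age (spline) and prior screening utilization only, fitted on the same 70% training set and the same CRC-or-adenoma label, and scored on the same hold-out.
3. Report paired differences in AUC and AUPRC, with 95% CIs, for best ML minus PennChart and for best ML minus the refitted two-predictor model.
4. Base any statement that ML or the added predictors improve on age and screening history on the second contrast.

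The cost is one extra regression on data already assembled, with no new patients. The reported advantage of ML may turn out smaller.

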Improving Colorectal Cancer Screening in Racially Diverse Zip Codes Using Navigation and Machine Learning (PCSNaP)

NCT05383976

October 26, 2021

Program Director/Principal Investigator (Last, First, Middle): [name]

PA-20-272 "Administrative Supplements to Existing Grants and Cooperative Agreements (Parent Admin Supplement)": A Feasibility Study to Improve Colorectal Cancer Screening among Racially Diverse Zip Codes in a Persistent Poverty County using Navigation and Machine Learning Predictive Algorithms

Abstract

The overarching goals of this Administrative Supplement to Existing NIH Grants and Cooperative Agreements (PA-20-272, Parent Admin Supplement) is to support the Abramson Cancer Center (ACC) of the University of Pennsylvania in carrying out its mission to increase colorectal cancer (CRC) screening completion among high-risk individuals living in a persistent poverty county by designing, conducting, disseminating and evaluating an electronic health record-based automated identification program to target effective, culturally-sensitive CRC screening navigation to individuals who have not completed an ordered colonoscopy or fecal immunochemical test (FIT).

Specifically, the goals of this supplement are to: 1) Adapt a previously validated electronic health record (EHR)-based machine learning algorithm to predict CRC detection by retraining the model using data from patients seen in primary care clinics serving zip codes with a high proportion of racial and ethnic minorities living in Philadelphia County, a persistent poverty county; and 2) Implement and evaluate the feasibility and effectiveness of an algorithm-based CRC navigation program to increase colorectal cancer screening among patients in Philadelphia county who are at high risk of CRC and have uncompleted colonoscopies.

Together, these novel projects aim to be the first to combine use machine learning algorithms and patient navigation to increase guideline-based cancer screening in order to reduce the burden of CRC among high-risk individuals living in a persistent poverty county through targeted, culturally-sensitive navigation that addresses social factors that prevent CRC screening. This study will generate preliminary data in support of an R01 application to scale algorithm-informed cancer screening navigation in persistent poverty areas.

Specific Aims

[figure not shown]

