Cohort. The cohort will consist of patients residing in 18 zip codes in Western and Southwestern Philadelphia who have primary care providers in 4 Penn Medicine Internal Medicine practices and 3 Penn Medicine Family Medicine Practices. Patients will have had a colonoscopy order placed in the past 6 months and have not scheduled, cancelled, or no-showed to their colonoscopy.

Intervention. This intervention will utilize the existing Penn Medicine CRC patient navigation program; administrative supplement funding will be used to expand the staff from 1.5 FTE to 2.5 FTE. In the revised intervention, we will provide a monthly list of ~300 patients with unfilled colonoscopies, risk-stratified according

Program Director/Principal Investigator (Last, First, Middle): [name]

the ML algorithm and select high-risk criteria.¹⁰ The navigation team will prioritize timely outreach and navigation to high-risk patients according to a script that communicates risk.

Outcome. The co-primary outcomes, measured within 3 months of enrollment, will be (1) enrollment in navigator program (feasibility); (2) completion of colonoscopy or FIT testing; and (3) adenoma detection rate.

Analysis Plan. We will use an intention-to-treat analysis. We will use propensity score matching using clinical and sociodemographic characteristics to create matched cohorts of patients between the intervention participants and historical controls from the same clinics in the year prior. We will then use logistic regression to assess the association between the intervention and the two primary outcomes, adjusted for age, gender, comorbidity, and area-level socioeconomic status.

Statistical Power. A sample of 344 participants (172 per group) will provide >90% power, assuming Type I error rate with a 2-sided α 0.05 and 50% dropout/refusal to participate to navigation, to detect a 20 percentage-point (pp) increase in colon cancer screening completion (40 \rightarrow 60%, SD 20%) in the intervention group.

Work plan and timeline

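### Aim 2 entry is tested on colonoscopy alone but completion is scored as colonoscopy or FIT, so a patient with a FIT between order and first listing can enter having already met the outcome

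*Combined protocol and SAP*

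**What the plan says.** All places are in the combined protocol and SAP.

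- **Entry** (Approach, Aim 2, Cohort): "Patients will have had a colonoscopy order placed in the past 6 months and have not scheduled, cancelled, or no-showed to their colonoscopy". There is no FIT condition.
- **List** (Aim 2, Intervention): "we will provide a monthly list of ~300 patients with unfilled colonoscopies". Again only colonoscopy is mentioned.
- **Outcome** (Aim 2, Outcome): the second co-primary is "completion of colonoscopy or FIT testing". The window is set by "The co-primary outcomes, measured within 3 months of enrollment".
- **Target population** (Abstract, opening paragraph): "individuals who have not completed an ordered colonoscopy or fecal immunochemical test (FIT"). Goal 2 of the same Abstract refers only to patients "who are at high risk of CRC and have uncompleted colonoscopies", so the Abstract is itself not uniform.
- **Existing program** (Existing Services): the services include a "mailed FIT test for average-risk patients who refuse colonoscopy".
- **Comparator** (Aim 2, Analysis Plan): propensity-matched historical controls from the same clinics in the preceding year. Their entry rule and time zero are not stated, and prior FIT is not named among the matching or adjustment variables.

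**The concern.** A completion rate should be computed among people who have not yet completed the thing being counted. Here the entry test and the outcome use different definitions of screening. A patient who declines colonoscopy and returns a FIT still has an unfilled colonoscopy order, and while that order is under six months old the patient satisfies the Cohort rule. If the FIT precedes first listing, the patient starts follow-up having already met the outcome.

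Such patients are foreseeable, because the running program mails FIT kits to average-risk patients who refuse colonoscopy. What happens to them in the analysis is unstated. Read literally, the 3-month window ignores the earlier FIT, and the patient counts as a completer only if tested again. An EHR extract that looks for any FIT result after the order would count the patient as a completer without anything happening after enrollment. Either way the denominator is not the at-risk population in the Abstract, and the comparison with historical controls inherits the problem.

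**Working it through.** **Inputs.** From Aim 2, Statistical Power: control completion 40%, intervention completion 60%, 172 per group, two-sided α 0.05. I take 40% and 60% to be the rates among patients with no earlier FIT. The share f of entrants with a FIT between order and first listing is not in the documents; I assume 0% to 20%.

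**The plan's own figure.** Two-proportion z-test with pooled variance under the null:

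power = Φ{[d√n − 1.96√(2p̄(1−p̄))] / √(p₁(1−p₁) + p₂(1−p₂))}

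With d = 0.20, n = 172, p̄ = 0.50: (2.623 − 1.386)/0.693 = 1.786, so power is 96.3%. This agrees with the stated figure of more than 90% if all 172 per group are analysed. With the plan's 50% loss applied to both groups (86 each) it is 75.1%. That shortfall is a separate matter and is not evidence for this point.

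**Effect of earlier FITs on each rate.** Let c be the proportion of prior-FIT patients who end up counted as completers:

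observed rate = p(1 − f) + f·c

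If the earlier FIT is ignored and nobody is retested, c = 0. If it is credited, c = 1. Some retesting falls in between.

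**Equal f and equal c in both groups.** The f·c term cancels, and the difference is (60 − 40)(1 − f) = 20(1 − f) points for any c.

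| assumed f, both groups | ignored, no retest | credited | difference | power, 172 per group |
|---|---|---|---|---|
| 0% | 40 v 60 | 40 v 60 | 20 | 96.3% |
| 5% | 38 v 57 | 43 v 62 | 19 | 94.5% |
| 10% | 36 v 54 | 46 v 64 | 18 | 92.2% |
| 15% | 34 v 51 | 49 v 66 | 17 | 89.4% |
| 20% | 32 v 48 | 52 v 68 | 16 | 86.1% |

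The power is the same under both rules because the pairs mirror each other about 50% (38 v 57 and 43 v 62, for instance). These power figures assume no other loss.

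**Unequal f.** Writing f_I and f_C for the intervention and control shares, the difference in points is

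- ignored, no retest: 20 − 60f_I + 40f_C
- credited: 20 + 40f_I − 60f_C

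| assumed shares | ignored, no retest | credited |
|---|---|---|
| 5% in intervention only | 20 − 3 = 17 | 20 + 2 = 22 |
| 5% in controls only | 20 + 2 = 22 | 20 − 3 = 17 |

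So the sign of the bias depends on which group has more such patients and on a counting rule that the plan does not state.

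**Cost of excluding them.** The analysed number falls to 172(1 − f): 163 per group at 5%, 146 at 15%. With the difference restored to 20 points, 90% power needs 130 per group (140 with continuity correction), so the exclusion alone does not exhaust the margin at these shares.

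**The case against.** The strongest reply is that the Abstract already points to people without a completed FIT, so the team may intend to remove them. The navigator workflow figure is not visible in the text available and may show how FIT returners leave the lists. This is fair as to intent. It does not repair the Cohort and list rules, which are the operative text and name colonoscopy only, as does goal 2.

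A second reply concerns timing, and it stands. The only FIT route described is a kit mailed after navigator contact. If time zero is first listing, a kit returned within the next 3 months is a legitimate success, not contamination. The problem is confined to FITs completed before first listing, for example through earlier navigation or outside the program.

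A reader might go further in three ways that the documents do not support:

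- *That the completion rate is depressed.* This needs earlier FITs to be ignored and few patients to be tested again. No such rule is stated, these patients still have an open colonoscopy order, and crediting the FIT raises the rate.
- *That added navigation staff produces a differential bias.* Extra staff mainly generates FITs after enrollment, which are outcomes. A contrast between Internal and Family Medicine practices is not in itself a contrast between periods, since controls come from the same clinics.
- *That a true 20 points would read as 13.* This needs, for example, 15% prior FIT in the intervention group against 5% in controls, with the FIT ignored and no retesting (51 v 38). No document supports a threefold difference. Reversing the shares gives 57 v 34, or 23 points.

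**Conclusion.** The defect is real: the entry rule admits patients who have already met co-primary (2), and it disagrees with the Abstract's opening description. Its size is unknown because no FIT frequency is given. With equal shares and the same handling in both groups, the cost is attenuation to 20(1 − f) points: 19 at an assumed 5% and 17 at 15%. With unequal shares the bias can go in either direction, and the documents do not show which. These figures rest on the planned 40% and 60% applying to patients without an earlier FIT. The distortion is probably modest, but the rule should be corrected before either cohort is extracted, because the result is meant to support a larger trial application.

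**What to change.** 1. Reconcile the Abstract (opening paragraph and goal 2) with the Aim 2 Cohort and Intervention paragraphs on whether a completed FIT removes a patient from the target population.
2. Define the index date as the date of first listing. For historical controls, use the first monthly list on which they would have appeared under the same rule.
3. In both cohorts, restrict the analysis set for co-primary (2) to patients with neither a completed colonoscopy nor a resulted FIT between the order date and the index date.
4. Enter each patient once, and apply the same time zero and 3-month window to both groups.
5. Report how many patients this rule removes in each cohort, so that f is known.

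This governs only who is analysed for one outcome; who receives outreach stays with the program. A separate stratum for patients with a positive earlier FIT is optional.

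The cost is one FIT-result-date filter applied to both extracts, a slightly smaller analysed cohort, and a denominator for co-primary (2) that differs from the outreach list and possibly from the other co-primaries. The report should state that difference.
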